6.4 Safety

The Investigator will evaluate safety by AE monitoring, physical examination, vital signs, laboratory tests, ECG, imaging and concomitant medication/surgery, as outlined in the Schedule of Assessments (Table 1 and Table 3).

6.4.1 Adverse Events

The Investigator is responsible for recording all AEs observed during the study period (main study phase and ET phase) including 4-week post-treatment follow-up.

Definition of an Adverse Event

An AE is defined as any untoward medical occurrence in a patient during the study; the event does not necessarily have a causal relationship with the treatment. This includes any newly occurring event or worsening of a preexisting condition (e.g., increase in its severity or frequency). An AE can therefore be any unfavorable and unintended sign (including an abnormal laboratory finding), symptom, or disease (new or exacerbated) temporally associated with the use of study treatment. Lack of efficacy or insufficient clinical response should not be recorded as an AE.

Events which meet the definition of an AE include:

- Any abnormal laboratory test results (hematology, clinical chemistry, or urinalysis) or other safety assessments (eg, ECG, radiological scans, vital signs measurements), including those that worsen from baseline, considered clinically significant in the medical and scientific judgment of the Investigator (ie, not related to progression of underlying disease).
- Exacerbation of a chronic or intermittent pre-existing condition including either an increase in frequency and/or intensity of the condition.
- New conditions detected or diagnosed after study treatment administration even though it may have been present before the start of the study.
- Signs, symptoms, or the clinical sequelae of a suspected drug-drug interaction.
- Signs, symptoms, or the clinical sequelae of a suspected overdose of either study treatment or a concomitant medication. Overdose per se will not be reported as an AE/SAE unless it is an intentional overdose taken with possible suicidal/self-harming intent. Such overdoses should be reported regardless of sequelae.

Events which **do not** meet the definition of an AE include:

- Any clinically significant abnormal laboratory findings or other abnormal safety assessments which are associated with the underlying disease, unless judged by the Investigator to be more severe than expected for the patient's condition. **Changes in laboratory findings that fulfil the definition of an AESI must ALWAYS be reported as an AESI (AND as an SAE if any seriousness criteria are also met).**
- The disease/disorder being studied or expected progression, signs, or symptoms of the disease/disorder being studied, unless more severe than expected for the patient's condition.
- Medical or surgical procedure (eg, endoscopy, appendectomy): the condition that leads to the procedure is the AE.
- Situations in which an untoward medical occurrence did not occur (social and/or convenience admission to a hospital).
- Anticipated day-to-day fluctuations of pre-existing disease(s) or condition(s) present or detected at the start of the study that do not worsen.

Definition of a Serious Adverse Event

An SAE is any untoward medical occurrence (whether considered to be related to study drug or not) that at any dose:

- Results in death

- Is life-threatening (the patient is at a risk of death at the time of the event; it does not refer to an event which hypothetically might have caused death if it were more severe)
- Requires inpatient hospitalization or prolongation of existing hospitalization: Hospital admissions and/or surgical operations planned before or during a study are not considered AEs if the illness or disease existed before the patient was enrolled in the study, provided that it did not deteriorate in an unexpected way during the study
- Results in persistent or significant disability/incapacity
- Is a congenital abnormality/birth defect
- Other: Medically significant events, which do not meet any of the criteria above, but may jeopardize the patient and may require medical or surgical intervention to prevent one of the other serious outcomes listed in the definition above. Examples of such events are blood dyscrasias (e.g., neutropenia or anaemia requiring blood transfusion) or convulsions that do not result in hospitalization.

An adverse drug reaction (ADR) is defined as any noxious and/or unintended response to a medicinal product related to any dose.

An unexpected ADR is defined as any adverse reaction, the nature of which is not consistent with the applicable product information. The Reference Safety Information Section of the IB identifies expected ADRs.

Each AE is to be evaluated for duration, severity, seriousness and causal relationship to the investigational drug. The action taken and the outcome must also be recorded.

Adverse Events of Special Interest

An AESI is defined as a serious or non-serious event of scientific and medical concern specific to the investigational product, for which ongoing monitoring and rapid communication by the Investigator to the Sponsor is necessary.

All AESIs will be recorded on the Adverse Event form in the eCRF, and in source documents. Any AESI which occurs during this study, whether or not related to the study drug, must be recorded in the electronic data capture (eDC) system within 24 hours of study staff becoming aware of the event. This entry into the eDC system will automatically trigger an e-mail alert to the Sponsor and to the MM.

If for any reason it is not possible to record the AESI information electronically, i.e., the eCRF database is not functioning, record the AESI on the paper AESI reporting form and submit within 24 hours as described above.

As soon as it is possible to do so, any AESI reported via paper must be transcribed into the eCRF database according to instructions in the eCRF completion guidelines.

Paper CRF reports are to be submitted to the Sponsor (or an authorized representative). Contact details for submitting paper CRF AESI reports will be provided to each site, including telephone number, fax number, and an e-mail address.

In addition to the initial 24-hour report, additional information is required to be added to the eCRF or a paper report sent to the Sponsor (or an authorized representative) within 48 hours of the event. These timelines apply to initial reports of AESIs and to all follow-up reports.

Based on the findings of nonclinical and clinical studies the following are classified as AESIs:

[REDACTED]

[REDACTED]

[REDACTED]

[REDACTED]

[REDACTED]

[REDACTED]

[REDACTED]

[REDACTED]

[REDACTED]

Any hepatic AESI which meets biochemical Hy's Law criteria (i.e. ALT/AST > 3x ULN and total bilirubin > 2x ULN) or has transaminase elevations which meet CTCAE criteria grade 4 (i.e. ALT/AST > 20 x ULN), must be reported as a medically significant SAE and as an AESI, regardless of causality.

Please refer to the common terminology criteria for adverse event (CTCAE) V5.0 grading definitions (Table 6).

Table 6 CTCAE Grading for Study AESIs

PARAMETER	GRADE 2: MODERATE	GRADE 3: SEVERE	GRADE 4: POTENTIALLY LIFE-THREATENING
[REDACTED]	[REDACTED]	[REDACTED]	[REDACTED]
[REDACTED]	[REDACTED]	[REDACTED]	[REDACTED]
[REDACTED]	[REDACTED]	[REDACTED]	[REDACTED]
[REDACTED]	[REDACTED]	[REDACTED]	[REDACTED]
[REDACTED]	[REDACTED]	[REDACTED]	[REDACTED]
[REDACTED]	[REDACTED]	[REDACTED]	[REDACTED]
[REDACTED]	[REDACTED]	[REDACTED]	[REDACTED]
[REDACTED]	[REDACTED]	[REDACTED]	[REDACTED]
[REDACTED]	[REDACTED]	[REDACTED]	[REDACTED]
[REDACTED]	[REDACTED]	[REDACTED]	[REDACTED]
[REDACTED]	[REDACTED]	[REDACTED]	[REDACTED]
[REDACTED]	[REDACTED]	[REDACTED]	[REDACTED]
[REDACTED]	[REDACTED]	[REDACTED]	[REDACTED]
[REDACTED]	[REDACTED]	[REDACTED]	[REDACTED]

Severity

The severity of the AE will be characterized in accordance with CTCAE criteria (V5.0). If the AE is not defined by CTCAE criteria, the severity of the AE will be characterized as “mild, moderate or severe” according to the following definitions:

- Mild events are usually transient and do not interfere with the patient’s daily activities
- Moderate events introduce a low level of inconvenience or concern to the patient and may interfere with daily activities
- Severe events interrupt the patient’s usual daily activity.

Relationship

The causal relationship between the study drug and the AE has to be characterized as unrelated, unlikely, possible, probable or unknown (unable to judge).

Events can be classified as “unrelated” if there is not a reasonable possibility that the study drug caused the AE.

An “unlikely” relationship suggests that only a remote connection exists between the study drug and the reported AE. Other conditions, including chronic illness, progression or expression of the disease state or reaction to concomitant medication, appear to explain the reported AE.

A “possible” relationship suggests that the association of the AE with the study drug is uncertain; however, the AE is not reasonably supported by other conditions.

A “probable” relationship suggests that a reasonable temporal sequence of the AE with drug administration exists and, in the Investigator’s clinical judgment, it is likely that a causal relationship exists between the drug administration and the AE, and other conditions (concurrent illness, progression or expression of disease state or concomitant medication reactions) do not appear to explain the AE.

All efforts should be made to classify the AE according to the above categories. The category “unknown” (unable to judge) may be used only if the causality is not assessable, e.g., because of insufficient evidence, conflicting evidence, conflicting data, or poor documentation.

All AEs encountered during the clinical study will be reported in the eCRF. If possible, a diagnosis should be documented rather than a list of individual signs and symptoms. All AEs should be recorded in English.

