6.4.1.1 Reporting of Adverse Events

All AEs which occur after the patient has provided informed consent, regardless of severity and whether or not they occurred during study enrolment, treatment or follow-up, are to be recorded on the appropriate AE pages (either ‘serious’ or ‘non-serious’) in the eCRF. The Investigator should complete all the details requested including dates of onset, severity, action taken, outcome and relationship to study drug. Each event should be recorded separately.

Each AE will be assessed to determine whether it meets seriousness criteria. If the AE is considered serious, the Investigator should record this event in the eDC system within 24 hours of becoming aware of the event. This entry into the eDC system will automatically trigger an e-mail alert to the Sponsor and to the MM.

An event may qualify for expedited reporting to regulatory authorities if it is an SAE, unexpected per reference safety information and considered related (Suspected Unexpected Serious Adverse Reaction [SUSAR]) in line with relevant legislation. All Investigators will receive a safety letter

notifying them of relevant SUSAR reports. The Investigator should notify the Ethics Committee as soon as is practical, of serious events in writing where this is required by local regulatory authorities, and in accordance with the local institutional policy.

Any SAE, including death due to any cause, which occurs during this study, whether or not related to the study drug, must be reported immediately (within 24 hours of the study centre's knowledge of the event) in the eCRF. The report will contain as much available information concerning the SAE to enable the Sponsor (or an authorized representative) to file a report, which satisfies regulatory reporting requirements.

If for any reason it is not possible to record the SAE information electronically, i.e., the eCRF database is not functioning, record the SAE on the paper SAE reporting form and submit within 24 hours as described above.

— As soon as it is possible to do so, any SAE reported via paper must be transcribed into the eCRF database according to instructions in the eCRF completion guidelines.

— If an SAE has been reported via a paper form because the eCRF database has been locked, no further action is necessary.

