18.1.1.2. Relationship to Study Medication

Relationship, as indicated by the Investigator, is classed as “unrelated”, “unlikely related”, “possibly related”, “probably related”, or “unknown” (increasing severity of relationship). A “related” TEAE is defined as a TEAE with a relationship to study treatment as “possibly related” or “probably related”. TEAEs with a missing or “unknown” relationship to study treatment will be regarded as “probably related” to study treatment. If a patient reports the same AE more than once within that SOC/ PT, the AE with the worst case relationship to study treatment will be used in

Document: \\ieedc-vnasc01\BIOSdata\F2G\F901318\ [Redacted]
Author: [Redacted] Version Number: 3.0
Version Date: 06Apr2023
Template No.: CS_TP_BS016 Revision 6 Reference: CS_WI_BS005
Effective Date: 02Dec2019

the corresponding relationship summaries.

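### The causality scale has no related category for an adverse event with both a plausible drug cause and a reasonable alternative, so related-event counts turn on an arbitrary coding choice

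*Protocol*

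**What the plan says.** Protocol Section 6.4.1, under Relationship, gives the Investigator five categories.

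- *Unrelated* applies "if there is not a reasonable possibility that the study drug caused the AE".
- *Unlikely* is defined first by the words "relationship suggests that only a remote connection exists between the study drug and the reported AE". The definition continues: "Other conditions, including chronic illness, progression or expression of the disease state or reaction to concomitant medication, appear to explain the reported AE".
- *Possible* is defined by the words "relationship suggests that the association of the AE with the study drug is uncertain; however, the AE is not reasonably supported by other conditions".
- *Probable* needs a reasonable time sequence and a likely causal link, and adds that other conditions "do not appear to explain the AE".
- *Unknown* "may be used only if the causality is not assessable, e.g., because of insufficient evidence, conflicting evidence, conflicting data, or poor documentation". Sites are told to make every effort to use one of the other four first.

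SAP 18.1.1.2 turns these into an analysis variable. A related "TEAE is defined as a TEAE with a relationship to study treatment as" possibly or probably related. A missing or *unknown* relationship is treated as probably related. *Unlikely* and *unrelated* are not related.

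On expedited reporting, Protocol Section 6.4.1.1 states: "An event may qualify for expedited reporting to regulatory authorities if it is an SAE, unexpected per reference safety information and considered related". It does not say which of the five categories amount to being considered related.

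**The concern.** A four-step causality scale normally uses its middle step for events that the drug may have caused but something else may also explain. Here the absence of a reasonable alternative is a condition of both related steps, so the middle step is closed to those events.

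Such events are likely to be common in this trial. The host factors in Appendix 2 are neutropenia, allogeneic stem cell transplant, prolonged corticosteroids, T-cell immunosuppressants and inherited immunodeficiency. The synopsis permits concomitant cytostatic agents. There is no comparator arm (Section 4.2), hence no concurrent background rate against which to read the adverse event tables, and Investigator causality carries more weight than it would in a randomised trial. The analysis of the first 100 patients is meant to let the sponsor consider initial approval (Section 8.1; SAP 4.3), so its safety tables may be read closely.

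**Working it through.** No arithmetic applies to the definitions, and the plan states no figure to reproduce. The check is to run one case through the five categories.

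**Test case (hypothetical).** A non-hepatic event starts during F901318 treatment in a patient who is also receiving a cytostatic agent. The Investigator thinks the study drug is a realistic cause and the other drug is also a reasonable one.

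| Category | What its text requires | Does the case fit? | Status under SAP 18.1.1.2 |
|---|---|---|---|
| Unrelated | No reasonable possibility of a drug cause | No: there is such a possibility | Not related |
| Unlikely | Remote drug link, and another condition appears to explain the event | Second element arguably; first element no | Not related |
| Possible | Uncertain link, and no reasonable support from other conditions | No: another cause is reasonable | Related |
| Probable | Likely link, and other conditions do not appear to explain the event | No: another cause is reasonable | Related |
| Unknown | Causality not assessable, for example because evidence or data conflict | Only if two competing causes are read as conflicting evidence | Counted as probably related |

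**Step 1.** Both related categories fail, and for the same reason.

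**Step 2.** *Unrelated* fails because it requires the absence of any reasonable possibility.

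**Step 3.** Two imperfect homes remain. *Unlikely* is the only category whose text accepts an alternative explanation, but it understates the drug link. *Unknown* can be stretched to cover the case, but it is reserved for events that cannot be assessed, and sites are told to avoid it.

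**Step 4.** The two homes sit on opposite sides of the SAP's line. The same event is excluded from the related count under one and enters it at the highest level under the other.

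**Step 5.** The outputs affected are TEAEs by relationship (SAP 18.1.1), serious TEAEs by relationship (SAP 18.1.4) and the AESI tables by Investigator-determined relationship (SAP 18.1.6).

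**Step 6, a bound that can be tabulated.** For any row of these tables, let R be the patients counted as related under the SAP rule, and U the patients whose worst recorded relationship is *unlikely*. Counting *unlikely* as related gives R + U. U is therefore the largest amount by which coding gap events as *unlikely* can have lowered that row. Within R, let K be the patients counted only because the entry was *unknown* or missing; R − K is the count without that upgrade. The documents contain no values for R, U or K.

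**The case against.** Five objections have force.

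**The wording is narrower than a blanket exclusion.** A reader might infer that *possible* rules out any event that something else could explain. The text does not say that: it excludes events reasonably supported by other conditions, so a merely conceivable alternative leaves *possible* open. The gap concerns reasonable alternatives only.

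***Unlikely* is not forced, and the direction is not fixed.** An Investigator who sees more than a remote link can decline *unlikely*, and *unknown* expressly covers conflicting evidence. The SAP then raises the event to probably related. A reader might infer that the error always runs toward fewer related events; the SAP rule contradicts this. What stands is that downward is the expected direction if sites follow the instruction to avoid *unknown*.

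**SUSAR loss is not shown.** A reader might infer that unexpected serious events escape expedited reporting. Section 6.4.1.1 does not tie being considered related to particular categories, and it calls for reporting of every SAE within 24 hours whatever the causality, with an automatic alert to the sponsor and Medical Monitor. It also lists the Investigator's causality entry as preliminary. The sponsor may make its own assessment, although the visible text describes none. Section 6.4.1.4 uses a judgement of *possible* as the reporting threshold for a late infant death, which hints that *unlikely* would fall below the line, but no more than that.

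**Other oversight exists.** Hepatic AESIs go to the Hepatic Advisory Committee whatever the Investigator's causality (Section 6.4.4.3), and SAP 18.1.6 has a separate table by that committee's relationship. The IDSMB reviews adverse events at least every 6 months (Section 6.4.4.1), although the visible text gives it no case-level causality role. The AESI list is redacted, so the full reach of this oversight cannot be judged.

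**Nothing vanishes.** Events coded *unlikely* stay in the all-TEAE tables and in the breakdown by relationship. The tables of serious events, deaths and discontinuations are not restricted to related events. No decision rule in the visible text uses the related count.

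These points limit the consequences. They do not supply a related category for the test case.

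**Conclusion.** The defect in the definitions holds: neither related category admits an event with a plausible drug cause and a reasonable alternative. Whether such an event counts as related then depends on whether the site picks *unlikely* or *unknown*, neither of which fits well. The related counts among TEAEs, serious TEAEs and AESIs by Investigator relationship are therefore partly arbitrary. They are likely to be understated, on the assumption that sites apply the definitions as written and respect the instruction to avoid *unknown*.

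The size cannot be stated. It needs the share of events with two plausible causes and how sites code them, and the documents give neither; any percentage would rest on invented inputs. Escape from SUSAR reporting is a risk created by the missing mapping, not something the documents show to happen.

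**What to change.** 1. **Protocol Section 6.4.1.** Reword *possible* to mean a reasonable time relation to study drug where underlying disease, another condition or a concomitant medication may also explain the event. Keep the absence of an alternative explanation as the mark of *probable* only.
2. **Protocol Section 6.4.1.1.** State which categories count as related for SUSAR purposes, consistent with SAP 18.1.1.2, including how *unknown* is treated.
3. **SAP 18.1.** For events already coded, add a sensitivity table that counts *unlikely* TEAEs and serious TEAEs as related, beside the planned tables. A footnote giving the number counted as related only because the entry was *unknown* or missing would show movement in the other direction.

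The sensitivity table is preferable to asking sites to reconsider only SAEs scored *unlikely*. Such a query could move events in one direction only, and it would leave non-serious events under the old wording, so the tables would mix two definitions.

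The cost is protocol and eCRF-guideline wording, a site memo and one additional output from data already collected. The downside is that related-event counts, and possibly SUSAR counts, may become less favourable. The table is an upper bound for events coded *unlikely*, because it also sweeps in events for which that code was right, and it does not reach gap events coded *unrelated*.

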6.4.1.1 Reporting of Adverse Events

All AEs which occur after the patient has provided informed consent, regardless of severity and whether or not they occurred during study enrolment, treatment or follow-up, are to be recorded on the appropriate AE pages (either ‘serious’ or ‘non-serious’) in the eCRF. The Investigator should complete all the details requested including dates of onset, severity, action taken, outcome and relationship to study drug. Each event should be recorded separately.

Each AE will be assessed to determine whether it meets seriousness criteria. If the AE is considered serious, the Investigator should record this event in the eDC system within 24 hours of becoming aware of the event. This entry into the eDC system will automatically trigger an e-mail alert to the Sponsor and to the MM.

An event may qualify for expedited reporting to regulatory authorities if it is an SAE, unexpected per reference safety information and considered related (Suspected Unexpected Serious Adverse Reaction [SUSAR]) in line with relevant legislation. All Investigators will receive a safety letter

notifying them of relevant SUSAR reports. The Investigator should notify the Ethics Committee as soon as is practical, of serious events in writing where this is required by local regulatory authorities, and in accordance with the local institutional policy.

Any SAE, including death due to any cause, which occurs during this study, whether or not related to the study drug, must be reported immediately (within 24 hours of the study centre's knowledge of the event) in the eCRF. The report will contain as much available information concerning the SAE to enable the Sponsor (or an authorized representative) to file a report, which satisfies regulatory reporting requirements.

If for any reason it is not possible to record the SAE information electronically, i.e., the eCRF database is not functioning, record the SAE on the paper SAE reporting form and submit within 24 hours as described above.

— As soon as it is possible to do so, any SAE reported via paper must be transcribed into the eCRF database according to instructions in the eCRF completion guidelines.

— If an SAE has been reported via a paper form because the eCRF database has been locked, no further action is necessary.

Paper CRF reports are to be submitted by telephone or fax to the Sponsor (or an authorized representative). Contact details for submitting paper CRF SAE reports will be provided to each site, including telephone number, fax number, and an e-mail address.

In addition to the initial 24-hour report, additional information is required to be added to the eCRF or a paper report sent to the Sponsor (or an authorized representative) via fax or mail within 48 hours of the event. These timelines apply to initial reports of SAEs and to all follow-up reports.

All SAEs will be recorded on the SAE Report form, the Adverse Events form in the eCRF, and source documents. Criteria for documenting the relationship to study drug as well as severity and outcome will be the same as those previously described.

All SAEs that are spontaneously reported within 30 days of a patient's last visit (EOS visit) are to be collected and reported as previously described.

The information must include the following as a minimum:

- Name, address and telephone number of the reporting Investigator.
- Investigational product and study code.
- Patient identification number, initials, sex and date of birth.
- Description of the AE, measures taken and outcome.

- Preliminary classification of causal relationship by the Investigator.

In the case of fatal or life-threatening events, the Investigator should immediately telephone the Sponsor's Safety Surveillance and Reporting Unit (or an authorized representative). Contact details will be provided to the site. Additional follow-up information should be completed on an SAE follow-up form with a copy sent to the Sponsor (or an authorized representative) and the original placed in the SAE section of the eCRF binder.

